5.3 Lifestyle considerations

For the duration of the study, participants should be informed and reminded of the restrictions outlined in this section.

5.3.1 Meals and dietary restrictions

CCI

5.3.1.1 Dietary restrictions and smoking

Participants should be encouraged to maintain a healthy diet and abstain from the use of alcohol or recreational drugs. Change in smoking status from parent study (CLTP001A12201) will be collected as part of the CRF.

5.3.2 Activity

No significant change in physical exercise program from the beginning of the study until after Study Completion evaluation.

5.4 Screen failures

A screen failure occurs when a participant who consents to participate in the clinical study is subsequently found to be ineligible and therefore not entered in the study. A minimal set of screen failure information is required to ensure transparent reporting of screen failure participants to meet the Consolidated Standards of Reporting Trials (CONSORT) publishing requirements and to respond to queries from regulatory authorities. Information includes the screen failure details, eligibility criteria, and any serious adverse event (SAE).

5.4.1 Participant numbering

Each participant is identified in the study by a Participant Number (Participant No.), that is assigned when the participant is enrolled and is retained for the participant throughout his/her participation in the trial. The Participant No. consists of the Site Number (Site No.) (as assigned by Novartis to the investigative site) with a sequential participant number suffixed to it, so that each participant's participation is numbered uniquely across the entire database. Upon signing the informed consent form, the participant is assigned to the next sequential Participant No. available.

6 Study treatment(s) and concomitant therapy

6.1 Study treatment(s)

Table 6-1 Investigational drugs

Investigational Drug (Name and Strength)	Pharmaceutical Dosage Form	Route of Administration	Supply Type	Sponsor (Global or Local)
LTP001 [REDACTED] mg	CCI	Oral Use	Open-label, participant-specific kits	Global
LTP001 [REDACTED] mg		Oral Use	Open-label, participant-specific kits	Global

6.1.1 Additional study treatments

No other treatment beyond investigational drug is included in this trial.

6.2 Preparation, handling, storage, and accountability

Each study site will be supplied with study drug in packaging as described under Study treatment(s) [Table 6-1](#).

A unique medication number is printed on the study medication label.

Investigator staff will identify the study medication kits to dispense to the participant by contacting the IRT and obtaining the medication number(s). The study medication has a 2-part label (base plus tear-off label). Immediately before dispensing the medication kit to the participant, site personnel will detach the outer part of the label from the packaging and affix it to the source document.

Where delivery of IMP directly to a participant's secure off-site location (e.g. home) is permitted by national and local governing regulations then dispatch of IMP from the site to the participant will be performed under the accountability of the Investigator. The provisioning of supply will be for a maximum of a three-month supply. In this case, regular contacts (every 12 weeks or more frequently if needed) will occur between the site and the participant for instructional purposes, safety monitoring, and discussion of the participant's health status until the participant's next visit to the study site.

6.2.1 Handling of study treatment

Study treatment must be received by a designated person at the study site, handled and stored safely and properly and kept in a secured location to which only the Investigator and designated site personnel have access. Upon receipt, all study treatment must be stored according to the instructions specified on the labels.

Clinical supplies are to be dispensed only in accordance with the protocol. Technical complaints are to be reported to the respective Novartis Country Organization Quality Assurance.

Medication labels will be in the local language and comply with the legal requirements of each country. They will include storage conditions for the study treatment but no information about the participant except for the medication number.

The Investigator must maintain an accurate record of the shipment and dispensing of study treatment in a drug accountability log. Monitoring of drug accountability will be performed by field monitors during site or remote monitoring visits, and at the completion of the trial.

Since study treatment is administered at home and when at the clinical site, participants will be asked to return all unused study treatment and packaging at the end of the study or at the time of discontinuation of study treatment.

The site may destroy and document destruction of unused study treatment, drug labels and packaging, as appropriate in compliance with site processes, monitoring processes, and per local regulation/guidelines. Otherwise, the Investigator will return all unused study treatment, packaging, drug labels, and a copy of the completed drug accountability log to the Novartis monitor or to the Novartis address provided in the Investigator folder at each site.

6.2.2 Handling of other treatment

It should be checked at each visit if other concomitant PAH specific therapy has been kept stable as specified in [Section 6.8.1](#).

6.2.3 Instruction for prescribing and taking study treatment

LTP001 should be taken daily at approximately the same time each day **CCI**. On clinic visit days, the participant should take LTP001 during the clinic visit when instructed by the study staff. 6MWT and RHC assessment should be executed at approximately the same time after drug administration each time (tolerance window +/- 1 hour).

CCI

If vomiting occurs during the course of treatment, participants should not take the study treatment LTP001 again before the next scheduled dose.

Participants should be instructed not to make up missed doses. A missed dose is defined as a case when the full dose is not taken within 12 hours after the approximate time of the usual daily dosing. That day's dose should be omitted and the participant should continue treatment with the next scheduled dose.

The first day the participant is seen by an off-site health professional during the visit window, or the first day of a visit to the clinical site should be the dose recorded in the Dosage Form eCRF.

Novartis will provide the site with a participant study card to hand over to all study participants, which will state that the participant is participating in a clinical study and is receiving an investigational product. This participant study card will also include the contact information of the Study Doctor/Investigative Site. Designated study staff will instruct study participants to present this card to a medical care provider if they have any medical issues during the course of the study.

All kits of study treatment assigned by the IRT will be recorded in the IRT system.

6.3 Measures to minimize bias: randomization and blinding

6.3.1 Treatment assignment, randomization

Not applicable

6.3.2 Treatment blinding

Not applicable

6.3.3 Emergency breaking of assigned treatment code

Emergency code breaks are not applicable, as the study medication is open-label.

6.4 Study treatment compliance

The investigator must promote compliance by instructing the participant to take the study treatment exactly as prescribed and by stating that compliance is necessary for the participant's safety and the validity of the study. The participant must also be instructed to contact the investigator if he/she is unable for any reason to take the study treatment as prescribed. Compliance will be assessed by the investigator and/or study personnel at each visit using pill counts (if applicable) and information provided by the participant. This information should be captured in the source document at each visit. All study treatment dispensed and returned must be recorded in the Drug Accountability Log.

Remote treatment administration compliance will be assessed by the off-site healthcare professional and information provided to the Investigator and/or study personnel.

6.4.1 Recommended treatment of adverse events

At present, there is insufficient information to provide specific recommendations regarding treatment of adverse events (AEs). If participants experience a deterioration of their PAH condition, investigators should determine if they need to be treated with additional PAH directed therapy. Study treatment discontinuation criteria as defined in [Section 7.1](#) should be observed.

Medication used to treat AEs must be recorded on the appropriate CRF.

6.5 Dose modification

Investigational study treatment dose adjustments and/or interruptions are not permitted.

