10.5 Appendix 5: Liver safety monitoring

To ensure participant safety and enhance reliability in determining the hepatotoxic potential of an investigational drug, a standardized process for identification, monitoring and evaluation of liver events has to be followed.

Please refer to [Table 10-1](#) in Appendix 5 for complete definitions of liver laboratory triggers.

Once a participant is exposed to study treatment, every liver event defined in [Table 10-1](#) should be followed up by the Investigator or designated personnel at the trial site, as summarized below. Since deterioration of PAH may result in increases of liver values it should be checked if an increase of liver values might be secondary to a deterioration of right heart failure. Liver chemistry tests (i.e. ALT, AST, TBL, PT/INR, ALP and G-GT) to confirm elevation. Increased liver values considered secondary to deterioration of right heart function are not considered liver events

- Liver chemistry repeats will be performed using the central laboratory. If results will not be available from the central laboratory, then the repeats can also be performed at a local laboratory to monitor the safety of the participant. If a liver event is subsequently reported, any local liver chemistry tests previously conducted that are associated with this event should have results recorded on the appropriate CRF.
- If the initial elevation is confirmed, close observation of the participant will be initiated, including consideration of treatment interruption if deemed appropriate.
- Discontinuation of the investigational drug (refer to the Discontinuation of study treatment [Section 7.1](#)), if appropriate
- Hospitalization of the participant if appropriate
- Causality assessment of the liver event
- Thorough follow-up of the liver event should include, as per the investigator's discretion to allow for a causality assessment: serology tests, imaging and pathology assessments, hepatologist's consultancy; obtaining more detailed history of symptoms and prior or concurrent diseases, history of concomitant drug use, exclusion of underlying liver disease.

All follow-up information and procedures performed must be recorded as appropriate in the eCRF.

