10.5.1 Liver event and laboratory trigger definitions & follow-up requirements

Table 10-1 Liver event and laboratory trigger definitions

	Definition/ threshold
Liver laboratory triggers If ALT, AST and total bilirubin normal at baseline:	
 • ALT or AST $> 5 \times$ ULN • ALP $> 2 \times$ ULN (in the absence of known bone pathology) • Total bilirubin $> 3 \times$ ULN (in the absence of known Gilbert syndrome) • ALT or AST $> 3 \times$ ULN and INR > 1.5 • Potential Hy's Law cases (defined as ALT or AST $> 3 \times$ ULN and Total bilirubin $> 2 \times$ ULN [mainly conjugated fraction] without notable increase in ALP to $> 2 \times$ ULN) • Any clinical event of jaundice (or equivalent term) • ALT or AST $> 3 \times$ ULN accompanied by (general) malaise, fatigue, abdominal pain, nausea, or vomiting, or rash with eosinophilia • Any adverse event potentially indicative of a liver toxicity
If ALT or AST abnormal at baseline:	
 • ALT or AST $> 3 \times$ baseline or > 300 U/L (whichever occurs first)

Notify Novartis study lead and medical lead of any finding of a liver event identified not explained by PAH worsening for further follow-up assessments.

Table 10-2 Follow up requirements for liver laboratory triggers - ALT, AST, TBL

	ALT	TBL	Liver Symptoms	Action
ALT increase without bilirubin increase:				
	If normal at baseline: ALT $> 3 \times$ ULN	Normal For participants with Gilbert's syndrome: No change in baseline TBL	None	
 • No change to study treatment • Measure ALT, AST, ALP, GGT, TBIL, INR, albumin, CK, and GLDH in 48-72 hours. • Follow-up for symptoms.
	If elevated at baseline: ALT $> 2 \times$ baseline or > 300 U/L (whichever occurs first)			

	ALT	TBL	Liver Symptoms	Action
	If normal at baseline: ALT > 5 x ULN for more than two weeks	Normal For participants with Gilbert's syndrome: No change in baseline TBL	None	
 • Interrupt study treatment • Measure ALT, AST, ALP, GGT, TBIL, INR, albumin, CK, and GLDH in 48-72 hours. • Follow-up for symptoms. • Initiate close monitoring and workup for competing etiologies. • Study treatment can be restarted only if another etiology is identified and liver enzymes return to baseline.
	If elevated at baseline: ALT > 3 x baseline or > 300 U/L (whichever occurs first) for more than two weeks			
	If normal at baseline: ALT > 8 x ULN	Normal	None	
ALT increase with bilirubin increase:				

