	If normal at baseline: ALT > 3 x ULN	TBL > 2 x ULN (or INR > 1.5) For participants with Gilbert's syndrome: Doubling of direct bilirubin	None	
	If elevated at baseline: ALT > 2 x baseline or > 300 U/L (whichever occurs first)			
	If normal at baseline: ALT > 3 x ULN	Normal or elevated	Severe fatigue, nausea, vomiting, right upper quadrant pain	
	If elevated at baseline: ALT > 2 x baseline or > 300 U/L (whichever occurs first)			

Table 10-3 Follow up requirements for liver laboratory triggers - Isolated Hyperbilirubinemia

Criteria	Actions required	Follow-up monitoring
Total Biliruin (isolated)		
>1.5 – 3.0 ULN	
 Maintain treatment Repeat LFTs within 48-72 hours 	Monitor LFTs weekly until resolution to ≤ Grade 1 or to baseline
> 3 - 10 × ULN (in the absence of known Gilbert syndrome)	
 Interrupt treatment Repeat LFT within 48-72 hours Hospitalize if clinically appropriate Establish causality Record the AE and contributing factors (e.g. conmeds, med hx, lab) in the appropriate CRF 	Monitor LFTs weekly until resolution to ≤ Grade 1 or to baseline (ALT, AST, total bilirubin, Alb, PT/INR, ALP and GGT) Test for hemolysis (e.g. reticulocytes, haptoglobin, unconjugated [indirect] bilirubin)
> 10 x ULN	
 Discontinue the study treatment immediately Hospitalize the participant Establish causality Record the AE and contributing factors (e.g. conmeds, med hx, lab) in the appropriate CRF 	ALT, AST, total bilirubin, Alb, PT/INR, ALP and GGT until resolution (frequency at Investigator discretion)
Any AE potentially indicative of a liver toxicity	
 Consider study treatment interruption or discontinuation Hospitalization if clinically appropriate Establish causality Record the AE and contributing factors (e.g. conmeds, med hx, lab) in the appropriate CRF 	Investigator discretion

Based on Investigator's discretion investigation(s) for contributing factors for the liver event can include: Serology tests, imaging and pathology assessments, hepatologist's consultancy; obtaining more detailed history of symptoms and prior or concurrent diseases, history of concomitant drug use, exclusion of underlying liver disease.

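### The protocol bans every interruption of study treatment in Sections 1.1 and 6.5, yet liver Tables 10-2 and 10-3 order interruption, and no exception clause reconciles them

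*Protocol*

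**What the plan says.** Section 6.5 of the protocol is a single sentence: "Investigational study treatment dose adjustments and/or interruptions are not permitted". The same sentence stands under Treatment Groups in Section 1.1. Neither place names an exception.

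Appendix 5 (Section 10.5) opens by saying that "a standardized process for identification, monitoring and evaluation of liver events has to be followed". Once an elevation is confirmed, it calls for close observation, "including consideration of treatment interruption if deemed appropriate". Discontinuation is a separate bullet.

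The tables in Section 10.5.1 go further:

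- Table 10-2, in the row "If normal at baseline: ALT > 5 x ULN for more than two weeks" with normal bilirubin and no symptoms, gives the action "Interrupt study treatment". The paired row for elevated baseline ALT (above 3 x baseline or above 300 U/L, again for more than two weeks) stands beside the same action. The stop is not final: "Study treatment can be restarted only if another etiology is identified and liver enzymes return to baseline".
- Table 10-3, for isolated total bilirubin above 3 and up to 10 x ULN without known Gilbert syndrome, says "Interrupt treatment". Above 10 x ULN it says "Discontinue the study treatment immediately".

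Section 7.1 tells the investigator to follow Appendices 5 and 6 after a liver or renal event, but only on the question of discontinuation. It defines discontinuation as a permanent stop, as does Section 10.2.2.

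**The concern.** Long-term safety is the primary objective, and LTP001 is first in class. The rule for what to do with study drug when liver tests rise should therefore have one reading. As written, an investigator whose participant meets a Table 10-2 or 10-3 trigger has two instructions that cannot both be obeyed.

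Three outcomes are possible:

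1. The site follows the table. This is the most likely course and the right one clinically, but the action contradicts Section 6.5 and can be logged as a deviation.
2. The site reads Section 6.5 together with Section 7.1, concludes that a pause is unavailable, and stops the participant permanently, although Table 10-2 would have allowed a restart.
3. The site obeys Section 6.5 literally and doses through the trigger. This is the least likely outcome and the worst for the participant.

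Sites could differ in which course they take. Counts of discontinuations and deviations would then partly reflect how each site read the protocol.

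**Working it through.** No arithmetic is needed to establish the point. The check is to set every protocol statement about pausing treatment side by side and look for a clause that reconciles them.

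| Place | Position on interruption |
|---|---|
| 1.1, Treatment Groups | Banned, no exception |
| 6.5 | Banned, no exception |
| 6.7 (overdose) | One of two options, with the medical monitor |
| 8.6.1 (AE action list) | A recordable action |
| 10.5 (text) | To be considered after a confirmed elevation |
| Table 10-2, sustained ALT rise | Ordered, with a restart rule |
| Table 10-3, bilirubin above 3 and up to 10 x ULN | Ordered, distinct from discontinuation |
| Table 10-3, AE suggesting liver toxicity | To be considered, as is discontinuation |

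**Count.** The ban stands in 2 places. Rows with a legible instruction to interrupt: 2 in Table 10-2 (normal and elevated baseline) + 1 in Table 10-3 = 3. The lower rows of Table 10-2 show no action in the text available. That may be a merged cell lost in PDF extraction, so they are not counted.

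**Could another clause reconcile them?**

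- *Section 7.1.* Its pointer to Appendix 5 covers discontinuation, defined there as permanent. Appendix 5 itself keeps the two actions apart, in separate bullets in Section 10.5 and separate rows in Table 10-3. A pointer about the permanent action is not an exception for the temporary one. Section 7.1 also lets LTP001 resume after a pregnancy termination, although it lists pregnancy under required discontinuation, so its own use of the term is loose.
- *Section 10.1.8.1.* It expects investigators to take immediate safety action even where that departs from the protocol, with notice to the sponsor and, under local rules, the IRB/IEC. This treats the action as a possible deviation and leaves the two texts in conflict. A planned step after more than two weeks of elevated ALT is also a poor fit for an immediate action.
- *Section 8.* It rules out waivers and exemptions, so a site has no informal route around Section 6.5.
- *Precedence.* No clause says that an appendix overrides the body of the protocol, or the reverse.

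Clauses that exempt the liver-table interruptions from the ban: 0.

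**One case followed through.** Take a participant with normal baseline ALT, whose ALT has been above 5 x ULN for more than two weeks, with normal bilirubin and no symptoms. Table 10-2 says pause, look for another cause, and restart if one is found and enzymes return to baseline. Section 6.5 says a pause is not allowed. Section 7.1 offers a permanent stop or nothing. The instructions are incompatible for this participant.

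**The case against.** The best reply is that a sensible site will not be misled. Section 6.5 sits under dose modification and can be read as a bar on elective changes, with Appendix 5 as the specific safety rule that prevails. Section 6.4.1, just before it, sends the reader to Section 7.1, which leads to Appendix 5. A site that reaches the trigger in Table 10-2 sees the restart condition in the same cell, so a mistaken permanent stop means disregarding the instruction being applied. Even a logged deviation would have little analytic effect. The only deviation listed in SAP Table 2-1 as excluding a participant concerns withdrawn consent, and the primary analysis is counts and summary statistics without models.

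Much of this stands. The safe reading is the likely one, the IRB/IEC consequence should not be pressed hard, and the effect on the planned summaries is probably small. The row count is also limited by the broken table: the two Table 10-2 rows are baseline variants beside one action cell.

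None of it removes the conflict. The safe reading has to be supplied by the reader, because the protocol does not state it. Taking the specific rule over the general one is a reasonable habit, but the ban is unqualified and appears twice.

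**Conclusion.** The concern holds. Sections 1.1 and 6.5 prohibit what Tables 10-2 and 10-3 require, and no current text reconciles them. The conflict is in intact current text, so neither redaction nor the amendment log explains it. It is an internal inconsistency in safety instructions and should be fixed.

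Its extent in the text is two unqualified bans against three rows with a legible order to interrupt. Its extent in participants is unknown: the documents give no incidence for these triggers, and Section 10.5 removes elevations judged secondary to worsening right heart function. For scale only, with about 40 participants expected, each avoidable permanent stop would be 1/40 = 2.5% of the cohort. The conclusion rests on the plain wording and on the protocol's own definition of discontinuation as permanent.

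**What to change.** At the next amendment:

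- In Sections 1.1 and 6.5, add to the prohibition: except as required by Section 10.5 (Tables 10-2 and 10-3) or Section 6.7, or as allowed by Section 7.1 for resumption after a pregnancy termination. A pause advised by the sponsor during a safety review under Section 7.5 could sensibly join the list.
- In the liver and renal bullet of Section 7.1, widen the pointer so that it covers interruption and restart as well as discontinuation.

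The cost is one clause in two places and one reworded bullet. No visits, procedures or data collection are added.

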6.6 Continued access to study treatment after the end of the study

Not applicable.

6.7 Treatment of overdose

In the event of an overdose, the Investigator should:

- Evaluate the participant to determine, in consultation with the medical monitor, whether study treatment should be interrupted or continued as per protocol. The participant should be checked for any adverse events and implementation of safety measures (e.g. additional visit for safety assessments/ additional assessments for safety) should be considered. The Novartis medical team, including the medical monitor, should be informed of any overdosing event.
- Document the quantity of the excess dose as well as the duration of the overdose.

